### **Study Abstract**

Item	Content
Project Title	An Exploratory Study on the Impact of Prolonged Postoperative Endotracheal Extubation Time on Postoperative Complications in Gastric Cancer Patients with Severe Obstructive Sleep Apnea
Study Objective	To investigate the impact of prolonging the time to postoperative endotracheal extubation on the incidence of postoperative complications in gastric cancer patients with severe obstructive sleep apnea.
Research Hypothesis	Prolonging the time to endotracheal extubation in gastric cancer patients with severe obstructive sleep apnea can reduce the incidence of postoperative complications.
Study Design	 Case-Control Study  Cohort Study 

Item	Content
Cross-Sectional Study	
	 Case Report / Case Series
Inclusion Criteria:	
 
1. Patients preoperatively diagnosed with resectable gastric cancer.
 
2. Patients without distant organ metastasis.
 
3. Patients with preoperative OCST or PSG results showing AHI >30 events/hour and Sa02 <80%.
 
4. Patients with cardiopulmonary function deemed suitable for surgery.
 
5. Patients aged 18–85 years.
 
6. Patients who voluntarily joined this study and provided written informed consent.
 

Exclusion Criteria:	
 
1. Patients with a history of or concurrent other malignant tumors.
 
2. Patients who underwent palliative resection.
 
3. Subjects who experienced acute cardiovascular or cerebrovascular events (e.g., acute cerebral infarction, acute coronary syndrome) within the past 3 months, or whose cardiovascular clinical symptoms/diseases are not well-controlled.
 
4. Patients with a history of psychotropic drug abuse that cannot be abstained, or those with psychiatric disorders.
 
5. Patients with concomitant diseases that, in the investigator's judgment, seriously endanger the patient's safety or affect the completion of the study.
 

Meet either (A + B) or C below.	
	
A: Presence of at least 1 of the following: (1) Patient complaints of sleepiness, non-restorative sleep, fatigue, or insomnia; (2) Waking from sleep due to choking or gasping; (3) Bed partner or other observer reports of habitual snoring, breathing interruptions, or both during sleep; (4) Diagnosed hypertension, mood disorder, cognitive dysfunction, coronary artery disease, cerebrovascular disease, congestive heart failure, atrial fibrillation, or type 2 diabetes.
 
B: PSG or OCST confirms <math>\geq 5</math> respiratory events/hour during monitoring, including obstructive apneas,

Item	Content
Sample Size & Justification	
mixed apneas, hypopneas, and respiratory effort-related arousals (RERAs).
 
C: PSG or OCST confirms <math>\geq 15</math> respiratory events/hour during monitoring, including obstructive apneas, mixed apneas, hypopneas, and RERAs.

Primary Exposure Factor	
The incidence of postoperative complications in gastric cancer patients with severe sleep apnea is the primary endpoint of this study. Based on previous large-scale literature reports, the incidence of perioperative cardiovascular complications in patients with severe sleep apnea undergoing non-cardiac surgery is 15% higher than in the normal population [8]. Using a power of 90% and a significance level of 5%, sample size estimation was performed using PASS, version 11 (NCSS, LLC). We need to recruit 93 patients per group. Accounting for loss to follow-up, dropouts, and other factors, we plan to include at least 120 patients per group.

Outcome Variables	
Time to endotracheal extubation

Follow-up Plan (For Cohort Studies)	
Incidence of short-term postoperative complications, graded using the Clavien-Dindo classification.
 
Routine follow-up examinations at 1, 3, 6, 9, and 12 months postoperatively. Collect routine follow-up indicators and assess the occurrence of postoperative complications.

Sample Collection	
 No  Yes
 
Brief description of tissue type and quantity: N/A

Non-Medical Purpose Examinations	
 No  Yes
 
e.g., unnecessary CT scans, contrast studies, lab tests, etc.: N/A

Statistical Methods	
Chi-square test or Fisher's exact test will be used to compare categorical variables. Continuous variables will be expressed as median and IQR if non-normally distributed and analyzed using the Mann-Whitney U test, or as mean (SD) if normally distributed and analyzed using the t-test.

Study Risk Self-Assessment	
 High-Risk Study  Medium-Risk Study  Low-Risk Study
 
Brief explanation: This is an observational study.

**Confidentiality Statement:**

The information contained in this study protocol is provided solely to the investigators of this project, the clinical research management committee, and relevant regulatory bodies for review. Disclosing any information to third parties unrelated to this study is strictly prohibited without the approval of the Principal Investigator.

**1. Research Background (State the rationale and significance of this study based on current domestic and international research)**

As one of the most common malignant tumors worldwide, gastric cancer ranks fifth in global cancer incidence and fourth in cancer mortality [1]. Current treatment for gastric cancer is comprehensive, primarily based on surgical treatment, with standard radical gastrectomy being the main procedure [2]. This process is complex, technically demanding, and carries relatively high surgical risks. Obstructive Sleep Apnea (OSA) is a sleep-related breathing disorder characterized by periodic partial or complete upper airway obstruction during sleep, manifesting as apneas and hypopneas [3]. Preliminary statistics indicate the overall prevalence of OSA among adults in China is 3.93% [4], yet the clinical diagnosis rate remains low. OSA is widely recognized as an independent risk factor for hypertension and metabolic syndrome [5, 6]. Reported prevalence of OSA among surgical patients is approximately 7%-10%, but can reach 68%-70% in high-risk populations (bariatric surgery or other major non-cardiac surgery). These patients have significantly increased perioperative complications and mortality [7, 8], especially severe sleep apnea. One cohort study reported the incidence of cardiovascular complications within 30 days after surgery in patients with severe sleep apnea was as high as 30.1% [8]. General anesthesia, sedatives, and postoperative analgesics are potent respiratory depressants; they can relax the upper airway dilator muscles and impair the ventilatory response to hypoxemia and hypercapnia. These effects exacerbate OSA. Concurrently, the hypoxemia caused by OSA can increase the incidence of postoperative complications in gastric cancer patients and may predispose them to postoperative cardiovascular complications [9]. Therefore, for gastric cancer patients with severe sleep apnea, strategies to reduce postoperative complications and adverse events are particularly important.

**2. Research Question & Objectives (Elucidate the scientific question and research objectives)**

To investigate the impact of prolonging the time to postoperative endotracheal extubation on the incidence of postoperative complications in gastric cancer patients with severe obstructive sleep apnea.

**3. Research Methods (This section should be elaborated in detail)**

## **Study Design**

This is a single-center, prospective cohort study. Starting June 2025, the study plans to enroll patients undergoing radical gastrectomy for gastric cancer in the Department of General Surgery of our hospital who also have severe obstructive sleep apnea. Based on the anesthesiologist's assessment during the perioperative period regarding sufficient metabolism of anesthetic agents and full patient awakening, patients will be divided into two groups regarding whether extubation time is prolonged (by 1-2 days): Exposure Group: Prolonged extubation time group; Non-Exposure Group: Non-prolonged extubation time group (extubation on the day of surgery group). Clinical data, intraoperative details, postoperative pathology, lymph node status, and postoperative complications will be recorded for all patients.

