## **Study Flowchart**

Gastric cancer patients with severe sleep apnea

-> Apply Inclusion/Exclusion Criteria

-> Undergo surgical treatment

-> Decision on prolonging extubation time?

text

Yes -> Exposure Group: Prolonged extubation time

text

No -> Non-Exposure Group: Non-prolonged extubation time

Compare complication rates between the two groups

-> Follow-up for 1 year

-> Compare complication rates between the two groups

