## **Data Collection and Management**

Preoperative patient status: General information (name, gender, age, BMI),

preoperative nutritional status, preoperative tumor marker levels, preoperative comorbidities, etc.

Postoperative recovery: Time to recovery of bowel function (first flatus, first oral water/fluid intake), postoperative complications (pulmonary infection, postoperative gastroparesis, postoperative reflux, inflammatory bowel obstruction, bleeding, perforation, anastomosis-related complications such as anastomotic leak, anastomotic stenosis, anastomotic bleeding, etc.), cardiovascular and cerebrovascular complications, etc.

Postoperative follow-up information: Patient review at 1, 3, 6, 9, and 12 months postoperatively, CT and gastroscopy results.

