### **Statistical Analysis Methods**

Chi-square test or Fisher's exact test will be used to compare categorical variables. Continuous variables will be expressed as median and IQR if non-normally distributed and analyzed using the Mann-Whitney U test, or as mean (SD) if normally distributed and analyzed using the t-test. Survival data will be analyzed using Kaplan-Meier curves. Enrollment is expected to be completed between June 2025 and June 2026. Follow-up is expected to be completed between June 2026 and June 2027.

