### **4. Feasibility Analysis**

This is an observational study requiring no additional medical procedures or expenses, making it technically and economically feasible.

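### The protocol does not say which readiness result leads to which extubation group, nor secures a record of readiness or of the reason for prolonging, so delayed readiness may be mixed with the effect of prolonging

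*Protocol*

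**What the plan says.** The objective (section 2) is "To investigate the impact of prolonging the time to postoperative endotracheal extubation on the incidence of postoperative complications". The hypothesis in the Study Abstract is that prolonging lowers the complication rate.

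Study Design bases the grouping on the anesthesiologist's perioperative judgement of whether the anesthetic has been cleared and on "full patient awakening, patients will be divided into two groups regarding whether extubation time is prolonged (by 1-2 days"). The non-exposed group is defined as patients extubated on the day of surgery. The Study Flowchart has one node, "Decision on prolonging extubation time", with a yes and a no branch and no criterion.

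The Study Abstract names the primary exposure factor as "Time to endotracheal extubation", so timing itself is covered.

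On data, Study Design states: "Clinical data, intraoperative details, postoperative pathology, lymph node status, and postoperative complications will be recorded for all patients". Data Collection and Management lists preoperative status, recovery items ("Postoperative recovery: Time to recovery of bowel function (first flatus, first oral water/fluid intake), postoperative complications" and others) and follow-up results. Two of these lists are left open-ended. Neither section names the readiness result, the time of readiness or the reason for prolonging.

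On analysis, Statistical Analysis Methods states: "Chi-square test or Fisher's exact test will be used to compare categorical variables".

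**The concern.** The objective concerns prolonging. It needs patients who could have been extubated on the day of surgery but were kept intubated, compared with similar patients who were extubated that day. The only stated basis for grouping is a readiness assessment, and its result is not mapped to a group.

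A patient who is slow to clear the anesthetic or to wake may have a different complication risk for reasons unrelated to how long the tube stays in. If such patients enter the prolonged group, the comparison attributes their risk to prolonging. It could then show harm where there is none, or understate a benefit. An analysis plan can stratify or adjust by readiness only if readiness and the reason were recorded at the time. Anesthesia records may show when a patient woke. Whether continued intubation was a choice is harder to reconstruct afterwards.

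**Working it through.** **Step 1: the text.** Three readings fit Study Design and the flowchart.

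- A: patients judged ready are kept intubated 1-2 days by clinical choice.
- B: patients judged not ready form the prolonged group.
- C: the prolonged group contains both.

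Reading A, and the ready part of C, bear on the objective. Three cues favour A: the abstract's hypothesis treats prolonging as something that can be done to reduce complications; prolonging by 1-2 days most naturally means beyond the point of readiness; and the flowchart node is a decision, not an assessment result. Against this, the sentence in Study Design makes the assessment the basis of the division, which also fits B or C. No other section settles it.

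**Step 2: possible size.** The protocol gives no figure for this point, so there is none to reproduce. What follows is an illustration.

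Inputs:

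- Risk in ready patients, extubated or kept: 30.1%. This is the rate for severe sleep apnea in Research Background. It counts cardiovascular complications only, not all Clavien-Dindo complications.
- Patients per group: 120 (Sample Size).
- Not-ready share of the prolonged group, f: assumed.
- Risk in not-ready patients, r: assumed, 45% to 60%.
- True effect of prolonging: assumed zero.

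Risk in the prolonged group = (1 - f) × 30.1% + f × r, so spurious harm = f × (r - 30.1%).

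- f = 0: 0 points.
- f = 25%, r = 45%: 0.25 × 14.9 = 3.7 points.
- f = 25%, r = 60%: 0.25 × 29.9 = 7.5 points.

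If r equals 30.1%, the distortion is zero at any f.

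The chance of a significant result uses the two-sided 5% test of two proportions, with pooled variance under the null. With d the difference, it is Φ((d - 1.96·s0)/s1) + Φ((-d - 1.96·s0)/s1), where s0 is the pooled and s1 the unpooled standard error.

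| f | r | Prolonged v same-day | d | s0 | s1 | Chance significant |
|---|---|---|---|---|---|---|
| 0 | any | 30.1% v 30.1% | 0 | 0.0592 | 0.0592 | 5.0% |
| 25% | 45% | 33.8% v 30.1% | 3.7 points | 0.0602 | 0.0602 | 9.5% |
| 25% | 60% | 37.6% v 30.1% | 7.5 points | 0.0611 | 0.0609 | 23.1% |

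**Step 3: dilution of a benefit.** Assume instead a 15-point benefit, that is, a risk of 15.1% in ready patients kept intubated. This is wholly assumed: the 15% under Sample Size contrasts severe sleep apnea with a normal population and is not an extubation effect. At f = 25%:

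- r = 45%: 30.1 - (0.75 × 15.1 + 0.25 × 45) = 7.5 points.
- r = 60%: 30.1 - (0.75 × 15.1 + 0.25 × 60) = 3.8 points.

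**Step 4: cost of restricting to ready patients.** Same test, assumed risks of 30.1% v 15.1%:

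| Same-day v prolonged, ready | Power |
|---|---|
| 120 v 120 | 79.7% |
| 120 v 108 (12 not ready) | 77.3% |
| 120 v 90 (30 not ready) | 72.6% |
| 120 v 60 (60 not ready) | 59.9% |

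**The case against.** The strongest reply is that reading A is the intended one. On the three cues above, the prolonged group would consist of ready patients kept intubated, and this distortion would be absent. That lowers the likelihood of harm, but it does not remove the ambiguity, because the grouping sentence still makes the assessment the basis of the division.

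A second reply is that the items may well be captured. Clinical data and intraoperative details are recorded for everyone, the lists are open-ended, and the study is prospective. This stands: the items are unlisted, not shown to be uncollected. The supportable claim is that the protocol does not secure them.

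A third reply is that the size is assumed. This also stands. Neither f nor r is in the documents, and the 30.1% is for a narrower outcome. The figures show what could happen, not what will.

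A fourth reply is that the choice of analysis set and of adjustment may sit in an analysis plan that is not shown. That is fair for the method. It is not an answer for the exposure definition or for data items that must be recorded prospectively.

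A reader might infer more: that the prolonged group is in fact made up of patients who were not ready, so that the study cannot answer its question, or that its result would point the wrong way. The documents support neither. They do not say which reading applies, and the direction and size of any distortion depend on shares and risks that they do not give.

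**Conclusion.** The point holds as one of exposure definition and data capture, and it should be corrected. Confidence is moderate because the text leans towards the harmless reading. The assessment-to-group rule is missing, no section names readiness or the reason for prolonging, and the stated group comparison is unadjusted. If not-ready patients enter the prolonged group, delayed readiness becomes part of the exposure.

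Under the assumptions in the working, a 25% not-ready share would produce a few points of spurious harm and raise the false-positive rate from 5.0% to somewhere between about two and nearly five times that level. If the prolonged group holds only ready patients, or if not-ready patients carry the same risk, nothing is distorted in this way. The textual finding does not depend on these numbers.

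**What to change.** - **Study Design and Study Flowchart:** define the exposed group as patients judged ready on the day of surgery but kept intubated 1-2 days by the treating team's usual-care decision. State how patients not ready that day are handled. If usual care keeps no ready patients intubated, say that the study describes delayed readiness.
- **Data Collection and Management:** list the time the patient was judged ready, the actual extubation time, and the reason for prolonging recorded at the time (not ready, or ready but kept).
- **Analysis:** report the comparison among patients ready on the day of surgery, with not-ready patients shown separately. This may be the primary analysis or a prespecified analysis beside it; either is acceptable.
- **Interpretation:** state that clinicians still select which ready patients stay intubated, so confounding by indication remains and the result is an association.

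The cost is two new record fields (time judged ready and reason), one item already named as the exposure factor, and a few sentences. No procedure is added, so the feasibility statement ("This is an observational study requiring no additional medical procedures or expenses, making it technically and economically feasible") still holds. If the restricted comparison is made primary, it has fewer patients: under the assumed risks, power falls from 79.7% to 72.6% if 30 of 120 are not ready. The Timeline puts the start of enrollment at June 2025, so the fields should be added promptly; reasons not recorded at the time may be lost. Nothing here takes a position on when patients should be extubated.

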## **Study Variables (Factors) and Measurement**

Study Variable: Whether endotracheal extubation time is prolonged.

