## **Study Outcomes**

Incidence of short-term postoperative complications, graded using the Clavien-Dindo classification.

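### Exposure is defined partly by when the tube actually came out and partly by a decision, at no fixed time, so an early complication can both set the group and count as its outcome

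*Protocol*

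**What the plan says.** The Protocol describes the exposure in four places.

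- **Study Abstract.** The primary exposure factor is the time to extubation, a realised quantity. (The row labels of this table are shifted in the extracted text; the entry is read here as the exposure.)
- **Study Design.** Grouping is "Based on the anesthesiologist's assessment during the perioperative period regarding sufficient metabolism of anesthetic agents and full patient awakening", and "patients will be divided into two groups regarding whether extubation time is prolonged (by 1-2 days". The comparator is the "Non-prolonged extubation time group (extubation on the day of surgery group", which describes what happened to the patient.
- **Study Variables (Factors) and Measurement.** "Study Variable: Whether endotracheal extubation time is prolonged". This fits either reading.
- **Study Flowchart.** After surgery, patients branch on "Decision on prolonging extubation time".

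The outcome is "Incidence of short-term postoperative complications, graded using the Clavien-Dindo classification", with no stated start of counting. Data Collection and Management lists events such as "inflammatory bowel obstruction, bleeding, perforation", together with cardiovascular and cerebrovascular complications. It does not set aside events that occur before the group is fixed. On recording, Study Design says "Clinical data, intraoperative details, postoperative pathology, lymph node status, and postoperative complications will be recorded for all patients". Neither section names the time of the extubation decision or the reason for prolongation.

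**The concern.** In a cohort study the exposure should be settled before the outcome starts to count. Here the wording allows the order to be reversed: a complication in the first hours keeps the tube in, the patient is therefore classed as prolonged, and the same complication is counted as an outcome of prolongation. That is reverse causation. Adjustment for baseline covariates cannot remove it, because the event arises after baseline and determines the exposure. The chi-square or Fisher comparison in Statistical Analysis Methods counts the event in whichever group the patient was placed.

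At stake is the primary comparison. The study hypothesis is that prolongation reduces complications. This mechanism inflates the exposed group's rate and lowers the other group's, so it could hide a real benefit or suggest harm where there is none. If the decision time and reason are not captured as patients are treated, a later analysis plan may be unable to separate the two kinds of prolongation.

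**Working it through.** The Protocol gives no figure on this point, so there is none to reproduce. The check has two parts.

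**1. The wording applied to one patient.** A patient is meant to be extubated on the day of surgery, bleeds before extubation, and stays intubated overnight.

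- By realised time (Study Abstract; comparator label in Study Design): not extubated on the day of surgery, so exposed.
- By the decision (Study Flowchart): unexposed if the decision was taken before the bleed, exposed if it was taken or revised afterwards. No time is given, so the result is undetermined.
- Outcome: bleeding is a listed postoperative complication and counts in either case.

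The only time anchor is the anesthesiologist's assessment, placed somewhere in the perioperative period. Study Design does not say that both groups must have passed that assessment, or that a tube kept in because of a complication is not prolongation. It also does not say where the one to two days start or how to class a longer duration.

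**2. Illustration of size.** Inputs:

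- N = 240 (Sample Size section).
- P = 0.301, borrowed from Research Background, where it is a 30-day cardiovascular rate in severe sleep apnea. P = 0.15 is an assumed alternative.
- f, the share of all patients classed as exposed because of an early complication: 1%, 2% or 5%. This is an assumption; the document gives nothing on it.
- No true effect; the remaining patients split evenly.

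Formulas:

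- Risk among the rest: r = (P − f)/(1 − f). This is also the unexposed rate.
- Group sizes: n1 = N[f + (1 − f)/2] and n0 = N(1 − f)/2.
- Exposed rate: p1 = [f + r(1 − f)/2] / [f + (1 − f)/2].
- Share of all complications involved: f/P.
- Rejection: two-sided 5% pooled z test, normal approximation.

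Worked case, P = 0.301, f = 0.05:

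- r = 0.251/0.95 = 0.264; n1 = 12 + 114 = 126; n0 = 114.
- p1 = (12 + 114 × 0.2642)/126 = 42.1/126 = 0.334; difference = 0.334 − 0.264 = 7.0 points.
- Null standard error = √[0.301 × 0.699 × (1/126 + 1/114)] = 0.0593; unpooled standard error = 0.0589.
- Upper-tail rejection = Φ[(0.0701 − 1.96 × 0.0593)/0.0589] = 0.217. The lower tail adds 0.001, giving 0.218.

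| P | f (patients of 240) | share of all complications | exposed vs unexposed | spurious excess | rejection |
|---|---|---|---|---|---|
| 30.1% | 1% (2.4) | 3% | 30.8% vs 29.4% | 1.4 points | 6% |
| 30.1% | 2% (4.8) | 7% | 31.5% vs 28.7% | 2.8 points | 8% |
| 30.1% | 5% (12) | 17% | 33.4% vs 26.4% | 7.0 points | 22% |
| 15% | 5% (12) | 33% | 19.0% vs 10.5% | 8.5 points | 45% |

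With only the 186 evaluable patients that the Sample Size section requires (2 × 93), the two 5% rows give 18% and 37% rejection instead of 22% and 45%.

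**The case against.** The strongest reply is that the sections fit one natural reading: surgery, then an assessment of drug clearance and awakening, then an elective choice to prolong or not. On that reading the day-of-surgery wording is only a gloss on the non-prolonged group, and the objective itself speaks of prolonging, which is a strategy. This is a fair reading, and if grouping were locked at that assessment most of the overlap would go. The text does not lock it. The sentence could equally mean that patients who fail the assessment form the prolonged group, and the Study Abstract's exposure is plainly a realised time.

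A second reply is that the size rests wholly on assumed shares. That stands. At a 30.1% rate, shares of 1% to 2% barely move the test, and the larger figures need 17% or 33% of all complications to hold the tube in.

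A third is that time zero and sensitivity analyses can be left to an analysis plan. That holds in part, but the definition of exposure and what is recorded prospectively belong in the protocol of a cohort study.

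Three stronger readings are tempting and are not supported.

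- A reader might infer that the Protocol makes complications set the group. It does not say so; it fails to rule it out.
- A reader might infer an opposite bias, because events after same-day extubation can fall only in the unexposed group. Those events are genuine outcomes of same-day extubation. Nothing described moves a patient into the unexposed group because of a complication.
- A reader might infer that decision time and reason will not be recorded. Items in Data Collection and Management end in an open-ended etc., so this is not established.

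**Conclusion.** The point holds as a defect of definition. The Study Abstract and the comparator label in Study Design use realised extubation time, the Study Flowchart uses a decision, Study Variables does not settle it, and no section fixes when the group is set or when complications start to count. Following the realised-time wording lets one event determine exposure and count as outcome, and that bias runs against prolongation.

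Its size is unknown. Under the assumptions above it ranges from little (1.4 points and about 6% rejection, if 1% of patients are affected at a 30.1% rate) to serious (7.0 points and 22% at 5%, or 8.5 points and 45% at 5% with a 15% rate). The upper figures should always be read with the share of complications that they imply. The case for correction rests on the conflict in the wording and the low cost of the remedy, not on the 5% scenarios.

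**What to change.** Reconcile the Study Abstract, Study Design, Study Variables and Study Flowchart to a single exposure definition: the extubation decision as recorded at one stated time zero, aligned in both groups, whatever the later duration of intubation.

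- Record the time of the decision, the readiness status if it was assessed, and the reason for prolongation.
- Count outcome complications from time zero and treat earlier events as baseline.
- As a sensitivity analysis, set apart patients whose prolongation was prompted by non-readiness or by an existing complication.

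The cost is two or three case-report fields and lower precision in the sensitivity analysis only. The 95% half-width for the risk difference is 1.96 × √[0.301 × 0.699 × (1/n1 + 1/120)]. It is 11.6 points with 120 exposed patients. It becomes 11.9, 12.5 or 14.2 points if 10%, 25% or 50% of them are set apart (n1 = 108, 90 or 60; assumed shares). If prolongation is mostly decided before readiness is assessed, the readiness part of that analysis may not be possible.

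The change stops the double counting. It does not remove confounding by indication, since patients chosen for prolongation may differ in risk, and the report should say so. It affects classification and recording only and proposes no rule for when to extubate.
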